LIBERATE – LIquid Biopsy Evaluation and Repository Development AT PrincEss Margaret
LFS – Li-Fraumeni Syndrome
Lynch/LS – Lynch Syndrome
MOHCCN - Marathon of Hope Cancer Centre Network
MTA - Material Transfer Agreement
MRN - Medical Record Number
NF1 – Neurofibromatosis Type 1
NPV - Negative Predictive Value
OICR - Ontario Institute for Cancer Research
PHI - Personal Health Information
PPV - Positive Predictive Value
SOP – Standard Operating Procedure
sWGS – Shallow Whole Genome Sequencing
TIDHI - Toronto Immune Digestive Health Institute
TP – Targeted Panel

Protocol Summary

CfDNA in Hereditary And High-risk Malignancies (CHARM) 2: Evaluating the Performance of a cfDNA Blood Test for Early Cancer Detection

Randomized Control Study

Sample Size

Total = 1000 patients with Hereditary Cancer Syndromes (HCS)

N = 500 (experimental arm)

N = 500 (control arm)

If other sites join our study, the appropriate MTAs and DTAs will be established, and samples collected at other institutions (who have institutional REB approval for the study) will be sent to UHN/OICR for analysis. Other sites may include: BC Cancer Agency, Mount Sinai Hospital, SickKids Hospital, Women's College Hospital, Sunnybrook Hospital, McGill Research Institute, Jewish General Hospital, IWK Health Centre, Eastern Health, Alberta University.

We will recruit up to 1000 patients at UHN.

Study Population

Our study focuses on patients with a known Hereditary Cancer Syndrome (HCS).

Accrual Period

January 2024 – December 2024

Study Design

Through the CHARM Consortium (www.charmconsortium.ca), we have shown that cell-free DNA (cfDNA) profiling can enable more frequent cancer surveillance from readily accessible blood collections and can detect cancer at the same time or earlier than clinical screening approaches. We are now conducting a prospective, multi-center, randomized control trial of cfDNA testing of 1,000 HCS carriers to 1) compare cancer detection rates with and without cfDNA testing, 2) assess cancer stage shift and clinical impact reducing mortality and morbidity cancers, and 3) assess impact of access to cfDNA results on patients' quality of life and psychological distress.

Study Duration

January 2024 – December 2031

Study Agent/ Intervention/ Procedure

cfDNA sequencing (on a blood sample), tri-annually for 4 years.

Primary Objective

Decrease the time to cancer detection and disease management in HCS carriers receiving cfDNA sequencing results compared to controls.

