2.0 Background Information

2.1 Background and Rationale

Early cancer detection is the surest path to survival, even cure. As cancer progresses, genetic changes continue to amass, thereby making late-stage cancers more aggressive, harder to eradicate, and more lethal. People who are affected by a hereditary cancer syndrome (HCS) have this lived experience, as they are born with a genetic change that puts them at high risk for developing multiple cancers throughout their lifetime. Over 200,000 Canadians harbor mutations in one of the >100 genes that cause an HCS, some facing a 100% lifetime risk of developing cancer^{1,2}. To find these cancers in time for effective treatment, all of these carriers undergo highly specific medical imaging and physical exams on a biannual or annual basis, often travelling 100s of kilometers at significant personal stress, expense, and time investment. Sadly, many of these patients receive late-stage cancer diagnoses, necessitating immediate and often radical surgeries, radiation treatments, or enrollment in experimental clinical trials.

People who carry an HCS genetic variant describe themselves as “ticking cancer time bombs” as they await the accumulation of mutations during their lifetime that trigger cancer development³. Depending on cancer type, individuals may be able to enroll in publicly-funded annual surveillance programs that are cancer-type specific and entail an array of comprehensive clinical exams and imaging modalities, such as full-body MRI, colonoscopies and mammograms. In HCS that predispose cancers for which early detection has not yet been possible, prophylactic surgeries are recommended, such as removal of breasts, ovaries, and fallopian tubes for carriers of Hereditary Breast and Ovarian Cancer (HBOC), removal of uterus and ovaries in Lynch Syndrome (LS), and gastrectomy for carriers of Hereditary Diffuse Gastric Cancer (HDGC)^{4,5,6}. These life-altering surgeries place a heavy psychological and physical burden on patients, particularly those of childbearing age who face uncertain timing of growing a family versus potential development of a cancer.

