3.1.2 Secondary Objectives

Our secondary objective is to establish whether cfDNA testing increases the frequency of cancers detected, in particular cancer types with limited detection rates using standard-of-care protocols (e.g., pancreatic cancer, endometrial cancer).

We will also assess patient and provider perceptions about cfDNA testing, and patient-reported outcomes including empowerment, distress, uncertainty, and anxiety.

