4.11 Endpoints

The endpoints of this study are:

1. To assess the performance of the cfDNA assay for cancer detection in patients with HCS, including assay sensitivity, specificity, PPV, and NPV. The test performance endpoint is a diagnosis of cancer and will be assessed at multiple points during the study (at a minimum yearly). Cancer diagnosis will be confirmed by imaging, pathology, or other confirmation deemed appropriate by the treating physician.
2. To assess the time to cancer diagnosis using cfDNA sequencing compared to controls.
3. To assess the detection rate of cancer with no standard-of-care screening available (e.g., pancreatic cancer, endometrial cancer) using cfDNA sequencing.
4. To assess patient reported outcomes (including anxiety, empowerment, distress, risk perception) using validated scales administered before, during, and after the study.

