If an abnormality is identified by a diagnostic procedure or imaging done in follow-up to a “positive” cfDNA assay result, additional investigations (e.g., imaging or biopsy) will be performed as part of the participants clinical care, and will be guided by the participant’s clinical team, or study investigator. Any biopsies and/or surgeries performed following identification of an abnormality by a diagnostic procedure or imaging, are no longer considered a study-related procedure or a risk detailed in this protocol.

Risks associated with the test result

There is a potential risk of receiving a “false positive” test result (i.e., a “positive” signal is detected on the cfDNA assay, but no cancer is present (i.e., no cancer is detected on any of the follow-up diagnostic investigations). This could result in unnecessary procedures and imaging, which can cause both physical and psychological risks to the participant.

There is also a potential risk of receiving a “false negative” test result (i.e., a “negative” signal is detected on the cfDNA assay, but cancer is present). This may result in non-compliance with a participant’s next standard-of-care cancer surveillance cycle, which

could cause a delay in a potential cancer diagnosis. During the consent process, and again at the time of cfDNA assay result disclosure, the study team will communicate to the participant that a “negative” cfDNA test result should not be interpreted as a definitive absence of cancer, and the cfDNA assay should not outweigh current clinical standard-of-care surveillance guidelines.

Risks associated with genetic testing

There is a risk that information gained from genetic research could be linked to the participant. To prevent this, all samples and data collected within this study will be identified by a unique study ID and all samples will also be tracked by a barcode. A list linking the study ID to participant information will only be made available to certain study team members, as permitted by REB. Samples will be held in a secure facility and will not be identified by the participant's name. The researchers believe the chance that someone will identify the participant is very small. Still, the risk may change in the future as people come up with new ways of tracing information and this will be communicated with the participant through the consent form.

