5.0 Selection of Subjects

This study will enroll 1000 participants across Canada. Up to 1000 will be enrolled at UHN. Participants will be recruited from the genetics, surgical, medical, and radiation oncology clinics. If other sites join our study, the appropriate MTAs and DTAs will be established, and samples collected at other institutions (who have institutional REB approval for the study) will be sent to UHN for analysis. We are still in the process of determining which other sites will be involved in our study. Other sites may include: BC Cancer Agency, Mount Sinai Hospital, SickKids Hospital, Women’s College Hospital, Sunnybrook Hospital, McGill Research Institute, Jewish General Hospital, IWK Health Centre, Eastern Health. If the patient receives care at more than one of the above sites, their medical records from any of the other sites can also be looked at, regardless of which site they are enrolled at for this study.

5.1 Subject inclusion criteria.

Patients must fulfill the following criteria:

1. Patients with a confirmed diagnosis of HBOC, LS, NF1, LFS, PALB2, and HDGC (i.e., patients with an identified pathogenic variant in the respective cancer predisposition gene, or patients with uninformative genetic testing but with a family history suggestive of the cancer predisposition syndrome).
2. Patients must be receiving standard-of-care clinical assessment for cancer by a managing physician under a provincial screening program or cancer surveillance protocol.
3. All patients must have signed and dated an informed consent form for this study.

5.2 Subject exclusion criteria.

1. Patients must not have a personal history of cancer diagnosed and treated within 3 years prior to the expected first sample collection date for this study. If a patient has a personal history of cancer, treatment must have been completed successfully at least 3 years prior to first study sample collection.
2. Patients diagnosed more than 3 years prior to the expected first sample collection date, but never been treated for the cancer.
3. Patients undergoing investigations for a clinical suspicion of cancer.
4. Patients who are not able to comply with the protocol (i.e., tri-annual blood sample collection if randomized into the experimental cohort).

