8.0 Statistics

We will compare the cancer detection rate between control and experimental cohorts. Analysis will be stratified by the type of the tumours detected within each HCS, as well as across the entire cohort. Between the cohorts, we will first compare the cancers detected to ascertain whether cfDNA testing results in a more sensitive detection of clinically confirmed cancers, as well as calculate negative and positive predictive values of cfDNA findings as confirmed by clinical testing (MRI, ultrasound, biopsy, protein biomarkers, etc.). This analysis will also ascertain whether cfDNA is more or less effective at detecting specific cancer types compared to standard-of-care screening alone.

We will also conduct comparisons that compare categorical (e.g. cancer stage) and continuous time course data (e.g. time to symptom development, time to treatment, and time on treatment). The first comparison is a stage shift analysis, whereby we will assess whether cancers are being detected at earlier stages using cfDNA versus screening results from the same programs. Categorical variables of stages I-IV within each cancer type as defined by NCCN criteria will be compared using Pearson's χ^2 test. Binary comparison of “early” and “late” stage across all cancer types will be performed using Fisher Exact test. The second comparison will be calculation of the time to first treatment relative to the date of the last annual clinical screening visit. This comparison of continuous variables using the t-test will establish whether triannual cfDNA testing accelerates off-cycle clinical follow-up and medical treatment compared to waiting for annual clinic visits. The third comparison will compare mortality and morbidity specifically for pancreas, esophagus, brain, lung, and stomach cancers. We will calculate the time between detection of a cancer and when patient manifest symptoms of cancer (morbidity 1), how long patients are afflicted with cancer symptoms after detection and during treatment (morbidity 2), and how long a patient undergoes treatment before succumbing to disease (mortality) or, in the case of effective treatments, the time until treatment is discontinued, or patients transition to the outpatient setting. Continuous variables will be compared by t-test.

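### The only mortality comparison is confined, without a stated reason, to five tumour sites and to treatment time among detected cases, so it cannot answer the unrestricted mortality aim in the Protocol Summary

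*Protocol*

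**What the plan says.** The Protocol Summary (Study Design) gives the second aim of the trial as to "assess cancer stage shift and clinical impact reducing mortality and morbidity cancers". It names no tumour site.

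Section 8.0 then sets out the one analysis of mortality: "The third comparison will compare mortality and morbidity specifically for pancreas, esophagus, brain, lung, and stomach cancers". For these cancers, mortality is defined as "how long a patient undergoes treatment before succumbing to disease (mortality"; for patients treated effectively, the time until treatment stops or care moves to the outpatient setting is used instead. Continuous measures are compared by t-test.

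The other comparisons in section 8.0 are wider. Detection is analysed by tumour type within each syndrome and over the whole cohort, early versus late stage over all cancer types, and time to first treatment without a site limit.

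Section 4.11 lists four endpoints, none of them mortality. The third reads: "To assess the detection rate of cancer with no standard-of-care screening available (e.g., pancreatic cancer, endometrial cancer) using cfDNA sequencing". Section 3.1.2 uses the same two cancers as examples. Section 2.1 links breast, ovary and fallopian tube to HBOC, uterus and ovary to Lynch syndrome, and stomach to HDGC. All three syndromes are enrolled under section 5.1.

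**The concern.** There are two problems, and they compound each other.

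**Scope.** The aim covers mortality in general, but the analysis covers five sites. The choice follows no rule that can be read from the protocol. If the rule were weak standard screening, endometrial cancer would stand beside pancreatic cancer. If it were syndrome risk, breast, ovary and uterus would be there. Lung cancer is mentioned nowhere else in the protocol text, and the esophagus otherwise only as a site of endoscopic perforation in section 4.13.1.

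**Measure.** Treatment time before death is a duration among people already diagnosed. It does not count deaths among people randomised. Who is diagnosed, with what and when, is what cfDNA testing is meant to alter, so the two groups compared are no longer those that randomisation made alike.

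At stake is whether the trial can say anything about deaths in either direction. Section 4.13.1 warns that a false-negative result "could cause a delay in a potential cancer diagnosis". If such a delay ended in death from breast, ovarian or endometrial cancer, that death would not enter the comparison.

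**Working it through.** The protocol gives no number of deaths, case fatality, cancer-site mix or enrolment share by syndrome, so there is no figure of its own to reproduce on this point.

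**1. What the measure can show.** Suppose testing brings detection and start of treatment forward by a time L and leaves the date of death unchanged. Treatment time before death then rises by L, while the number of deaths averted is 0. If instead testing prevents some deaths, those patients leave the group that dies, and the mean among the remaining deaths may move either way. A difference in this duration does not identify a difference in deaths.

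**2. Cancers expected.** Inputs: 500 per arm (section 4.1); 5% detected without cfDNA and up to 10% with it (section 8.0).

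- Control: 500 × 0.05 = 25.
- Experimental: 500 × 0.05 = 25, up to 500 × 0.10 = 50.
- Total: 50 to 75; at 5% versus 7%, 25 + 35 = 60.

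**3. Cases in the five sites.** Assume that 10% to 30% of cancers arise there.

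- Control: 25 × 0.10 to 25 × 0.30 = 2.5 to 7.5.
- Experimental: 25 × 0.10 to 50 × 0.30 = 2.5 to 15.

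For a two-sided t-test at 0.05, the difference needed for 80% power is 2.46 SD with 3 versus 5 cases, 1.66 SD with 5 versus 10, and 1.35 SD with 7 versus 15. The comparison of time to death has fewer cases still, since it needs a death.

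**4. Share of cancer deaths left out.** Let f be the share of cancers in the five sites, and c5 and co the case fatality inside and outside them. All three are assumptions.

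Share outside = (1 − f) × co / [(1 − f) × co + f × c5]

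| f | c5 | co | Calculation | Deaths outside |
|---|---|---|---|---|
| 10% | 50% | 20% | 0.18 / (0.18 + 0.05) | 78% |
| 20% | 60% | 10% | 0.08 / (0.08 + 0.12) | 40% |
| 30% | 80% | 10% | 0.07 / (0.07 + 0.24) | 23% |
| 50% | 80% | 5% | 0.025 / (0.025 + 0.40) | 6% |

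The first and last rows are the extremes for f of 10–50%, c5 of 50–80% and co of 5–20%.

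**5. Precision of a comparison by arm.** Take the second row with 60 cancers: deaths = 60 × (0.12 + 0.08) = 12. If they split 6 to 6, the risk is 6/500 = 1.2% per arm. The standard error of the difference is √(2 × 0.012 × 0.988 / 500) = 0.0069, so the 95% interval is about ±1.96 × 0.0069 = ±1.35 percentage points.

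**The case against.** The strongest reply is that mortality carries little weight in this plan. It is absent from the four endpoints and from the objectives in section 3.1, and rests on one loosely worded clause in the Protocol Summary. The list is fixed in advance and labelled as specific to its sites. It includes pancreas, one of the two named examples, and stomach, which section 2.1 ties to HDGC. The omitted cancers are still analysed for detection and stage, and section 7.0 reviews each year, at any site, the cancers found by standard screening that the assay missed. A delay in diagnosis could show there, though not as a death. All of this stands, and it lowers the severity.

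It is also fair that lengthening the list would not cure the measure. That is a reason to change the measure as well as the list.

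Some stronger readings are tempting but not supported:

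- A reader might infer that most cancer deaths go uncounted. The share depends wholly on assumed fatality. Equating the share of cancers omitted with the share of deaths omitted takes fatality to be the same in both groups.
- A reader might call HBOC and Lynch syndrome the main syndromes. No enrolment shares are given.
- A reader might call endometrial cancer the target of the trial. It is one of two examples, named for detection and not for mortality.
- A reader might add bowel cancer to the omissions tied to Lynch syndrome. Section 2.1 mentions colonoscopy only in general terms.
- A reader might say that lung and esophagus belong to no enrolled syndrome. The cohort-specific workflows are not at hand, so this cannot be settled.

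**Conclusion.** The point holds in limited form. The mortality analysis in section 8.0 is narrower than the aim in the Protocol Summary, for no stated reason, and leaves out endometrial cancer and the HBOC and Lynch cancers named in section 2.1. Its measure, treatment time among detected cases, cannot show whether testing changes deaths. These conclusions rest on the text alone.

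The numbers depend on assumptions. At a 10–30% share for the five sites, the comparison has roughly 3 to 8 control cases against 3 to 15. The proportion of cancer deaths left out could be anywhere from about 6% to 78%, so that most are missed can be neither confirmed nor ruled out. Severity is minor to moderate, because mortality is not a listed endpoint.

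**What to change.** In section 8.0, replace the mortality part of the third comparison with two counts by arm, from randomisation, in all randomised participants: death from cancer of any site, and death from any cause. Report the numbers and the rate difference with a 95% CI. Describe outcomes for the five sites, and for endometrial and ovarian cancer, without tests. Add date and cause of death to the list in section 4.8 (Collection of Clinical Data), which does not itemise them.

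The cost is wording and one data item, since section 4.8 already plans clinical data on all participants for up to 7 years from enrolment. One passage needs attention: section 5.3 stops data collection at withdrawal, so the text should say how withdrawn participants are counted. The downsides are the loss of the site-specific tests and a wide interval, about ±1.35 percentage points in the illustration above. Such an interval would show that the trial cannot settle mortality, but it would be a valid comparison of the randomised arms.

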4.8 Collection of Clinical Data

Clinical data will be collected from participants' medical record and the medical history and demographic questionnaires completed by participants following informed consent (please see "Demographics and Medical History Questionnaire"). Participants will be given the option to complete the questionnaire in person (e.g., if the consent process occurred in person), or electronically. If completed electronically, the questionnaire may be emailed to the participant, or the participant may complete the questionnaire via REDCap (a link will be emailed to them). If a patient is not able to complete the questionnaire electronically, a physical copy may be mailed to them with a return envelope. The questionnaires will record the patient's study ID only (name, DOB, MRN will not be recorded). Updates to questionnaire results may be collected by the study team over the course of the study.

If a participant receives care at more than one study site, their medical records from any of the other sites may also be looked at, regardless of which site they are enrolled at for this study. Sharing of any study records between sites for patients who have received care at multiple sites will only occur following execution of appropriate DTAs. Study team members may also request medical history information from participants directly, if not available in their medical records (e.g. by setting up a phone call). Additionally, study team members may ask a participant to complete a Release of Information (ROI) form (appended to this application), to request medical records from external hospitals/clinics.

The following clinical data will be captured over the course of this study for all participants:

- Demographic information (including date of birth, self-reported gender and sex assigned at birth, ethnicity).
- Genetic diagnosis and date.
- Past medical history, including but not limited to personal history of cancer, cancer risk factors, cancer screening history, pregnancy status, current medications, comorbidities.
- Cancer screening – results and dates of any cancer screening/diagnosis investigations done prior to, or during the study (including the diagnostic investigations done in follow-up to a positive cfDNA test result).

- For participants with a history of cancer or diagnosed with cancer during the study – pathology information, imaging and procedure results, treatment details.
- Family history of cancer.

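### The t-tests of symptom timing in section 8.0 leave out patients who never become symptomatic and read earlier death as less morbidity

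*Protocol*

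**What the plan says.** Section 8.0 of the protocol describes three supporting comparisons. On the last it says: "The third comparison will compare mortality and morbidity specifically for pancreas, esophagus, brain, lung, and stomach cancers". Three durations follow.

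- Morbidity 1: "We will calculate the time between detection of a cancer and when patient manifest symptoms of cancer (morbidity 1".
- Morbidity 2: "how long patients are afflicted with cancer symptoms after detection and during treatment (morbidity 2".
- Mortality: "how long a patient undergoes treatment before succumbing to disease (mortality", with a different end point for some patients: "in the case of effective treatments, the time until treatment is discontinued, or patients transition to the outpatient setting".

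The test is fixed in the same place: "Continuous variables will be compared by t-test". Earlier in the section, the time to symptoms is already classed with "continuous time course data (e.g. time to symptom development, time to treatment, and time on treatment".

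The section gives no value or censoring rule for a patient without symptoms, and no rule for death while symptomatic. For participants with a cancer diagnosis, the data list in section 4.8 names "pathology information, imaging and procedure results, treatment details". It has no field for the date symptoms start or resolve.

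**The concern.** A t-test needs a completed duration from each patient. Two groups do not supply a meaningful one.

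- **Morbidity 1.** A patient whose cancer is found and treated before symptoms appear has no symptom date, so no value. The same is true of a patient still symptom-free at the end of data collection, or one who dies first. The trial hopes to create more patients of the first kind, and the comparison removes them.
- **Morbidity 2.** Death ends the period with symptoms. A patient who dies soon after symptoms begin gets a short duration, which the comparison reads as mild morbidity.

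At stake is the reading of the clinical-impact aim in the Protocol Summary, which names mortality and morbidity. A working test could show no difference, or apparent harm, on these measures. An arm with faster deaths could look better on the second.

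**Working it through.** The protocol gives no figure for either morbidity measure, so there is none to reproduce. The check has two parts: how many patients are involved, and whether the measures can mislead.

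**Number of patients**

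Inputs from the protocol: 500 per arm (section 4.1) and diagnosis rates of 5% to 10% for all cancers (section 8.0).

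- All cancers per arm: 500 × 0.05 = 25 to 500 × 0.10 = 50.
- Assumption: 10% to 30% of these arise in the five named sites. Then 25 × 0.10 = 2.5 to 50 × 0.30 = 15, or about 3 to 15 per arm.

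**Morbidity 1 (all inputs assumed)**

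Time from detection to symptoms in controls is exponential with a median of 24 months, observed for 60 months. Its mean is θ = 24/ln 2 = 34.62 months.

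- Share with symptoms by 60 months: 1 − 2^(−60/24) = 0.823.
- Mean among those with a value: [34.62 − (60 + 34.62) × 0.1768]/0.823 = 21.7 months.
- Symptom-free time over 60 months, counting everyone: 34.62 × 0.823 = 28.5 months.

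Three versions of a genuine benefit in the experimental arm:

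| Who is spared symptoms | Share with a value, control v experimental | Mean seen by the t-test (months) | Symptom-free time over 60 months, everyone |
|---|---|---|---|
| A random half | 0.82 v 0.41 | 21.7 v 21.7 | 28.5 v 44.3 |
| Those otherwise symptomatic after 24 months | 0.82 v 0.50 | 21.7 v 10.6 | 28.5 v 35.3 |
| Those otherwise symptomatic after 36 months | 0.82 v 0.65 | 21.7 v 14.9 | 28.5 v 30.9 |

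The experimental figures follow from the same distribution.

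- Row 1: 0.5 × 60 + 0.5 × 28.5 = 44.3.
- Row 2: the mean below 24 months is [34.62 − 58.62 × 0.5]/0.5 = 10.6, and 0.5 × 60 + 0.5 × 10.6 = 35.3.
- Row 3: the mean below 36 months is [34.62 − 70.62 × 0.3536]/0.6464 = 14.9, and 0.3536 × 60 + 0.6464 × 14.94 = 30.9.

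In row 1 the benefit disappears from the t-test. In rows 2 and 3 it reverses sign.

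In row 1, with 2.5 to 15 relevant cancers in each arm, the t-test would use about 2 to 12 controls (0.823 × 2.5 to 0.823 × 15). In the experimental arm it would use about 1 to 6 (0.412 × 2.5 to 0.412 × 15).

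**Morbidity 2 (all inputs assumed)**

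Symptom duration if the patient lives is exponential with a median of 18 months, the same throughout. Only survival after symptom onset changes, with median m. The observed duration ends at resolution, death or 60 months. With rate λ = ln 2 × (1/18 + 1/m), the mean is (1 − e^(−60λ))/λ.

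| Median survival after symptom onset | Mean morbidity 2 (months) |
|---|---|
| No deaths | 23.4 |
| 24 months | 14.6 |
| 12 months | 10.4 |
| 6 months | 6.5 |

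The ordering does not depend on the numbers chosen. The observed duration is the smaller of time to resolution and time to death, so bringing death forward can only shorten it.

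**The case against.** The strongest reply is that this is a supporting comparison. It is not among the four endpoints in section 4.11, nor the outcome used for the power statement in section 8.0. Rules for censoring and missing values are commonly left to a statistical analysis plan. Mortality is also reported beside morbidity, so a reader would not see morbidity 2 alone.

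The first part stands and limits the weight of the point. The second stands only in part. The protocol itself fixes both the definitions and the t-test, and a plan that used censoring or counted death as an event would depart from that text. The third does not repair the measure. The mortality duration mixes time on treatment until death with time to stopping treatment or leaving inpatient care, and nothing links it to either morbidity measure.

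A reader might infer three stronger things that the protocol does not support.

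- **That the bias runs against cfDNA testing.** Direction depends on how many patients in each arm never become symptomatic, and on how many die and when. The protocol gives none of these. Section 8.0 also does not say how patients diagnosed because of symptoms are scored. If they count as zero or less, and are mostly controls, that would favour the experimental arm.
- **That about 25 cancers per arm are affected.** That is 5% of 500 for all cancers. This comparison covers five sites only.
- **That there is no way to obtain symptom data.** Sections 4.8 and 12.2 allow clinical history to be collected from records or from the participant. What is missing is a named symptom-date field, and field-level detail often sits in the case report form.

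**Conclusion.** The point holds as a fault in the analysis fixed by section 8.0. Followed as written, morbidity 1 excludes patients without an observed symptom date, including those with the best result, and morbidity 2 falls when death comes sooner. A true benefit can vanish or reverse.

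The size is not known. The month figures above rest on assumed exponential times and assumed shares spared symptoms, and serve only to show that the effect can be large. The count of about 3 to 15 relevant cancers per arm rests on the assumed 10% to 30% share. With so few patients, losing even a handful selectively matters.

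The consequence is confined to the morbidity part of the clinical-impact aim. It does not touch the four listed endpoints or the powered comparison. It should be corrected because the change is cheap and symptom dates are more reliable when recorded as they occur.

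**What to change.** In section 8.0, replace the t-tests of morbidity 1 and morbidity 2 with one outcome: time alive and free of symptoms from the five named cancers.

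- **Population and origin.** All randomised participants, by arm, measured from randomisation.
- **Window.** A fixed period that fits within the 5-year minimum follow-up. Section 4.1 counts that minimum from the first blood collection, which is optional for controls, so the window should be tied to randomisation in both arms.
- **Events.** Symptom onset and death both count, or death is handled as a competing event. Death before symptoms is then not credited as a success.
- **Censoring.** Withdrawn and event-free participants are censored at last contact. Section 5.3 stops data collection at withdrawal, so these participants must not be counted as symptom-free.
- **Comparison.** Restricted mean time, or a log-rank or Cox analysis.

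If symptom duration is still reported, rank death below any duration, or report days alive without symptoms over a fixed window.

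Add symptom onset and resolution dates to the section 4.8 data list, for diagnosed participants in both arms.

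The cost is a wording change and a few abstraction fields. Symptom dates taken from records will be imprecise. The effect will also be diluted by participants who never have one of these cancers: on the assumption above, those who do are 2.5/500 = 0.5% to 15/500 = 3% of an arm. The result should be read as supporting evidence with wide uncertainty.
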